## 5.6 Unblinding considerations

An unblinded study team (prescribing health care provider +/- coordinator) will be used to monitor sirolimus levels at 1 week and 1 month after baseline. Levels that increase by > 50% will lead to sirolimus dose reductions that will unblind the study participants. Such unblinding events will be reported to the research study monitor and be part of DSMB reporting.

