## 5.4 Visit Schedule

**The Baseline Visit** will begin with signing the informed consent. A history and physical examination, post-bronchodilator spirometry, 6 minute walk test distance, and blood samples will be obtained. Questionnaires will be completed and the patient will be randomized to imatinib mesylate, at an oral dose of 400 mg once daily, or placebo stratified on whether sirolimus has been used in the last month. A sirolimus level and VEGF-D level will be measured.

A 1 week trough sirolimus level and telephone call will be obtained on all subjects entering the study on sirolimus therapy.

**1 Month Visit-** Post-bronchodilator spirometry, 6 minute walk test distance, and blood samples will be obtained. Questionnaires will be completed. Sirolimus will be discontinued if used at baseline.

**2 Month Visit/ End of study-** Post-bronchodilator spirometry, 6 minute walk test distance, and blood samples will be obtained. Questionnaires will be completed. A sirolimus level will be obtained to assure drug cessation. The participant is returned to LAM therapy of their choice.

[figure not shown]

Figure 1. Study Schedule, Stratification and Randomization

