## 6. ETHICAL CONSIDERATIONS

This study will be initiated only after a thorough review by the MUSC IRB, the Columbia University IRB, and the Human Research Protection Office (HRPO) of the US Army Military Department. A written informed consent will be obtained from every participant in which known side effects of imatinib are described. Participants may participate in this study and request that their biosamples be anonymized and/or not stored after the study analysis is complete.

An important consideration for this study is that sirolimus is not currently FDA approved for LAM. However, it is estimated that 90% of individuals with LAM and low lung function are using this drug and efforts are underway by [name], principal investigator of the MILES trial and medical director of the LAM Foundation to obtain FDA approval via his IND for sirolimus. This study is submitted because no study in LAM will advance in this rare disease population unless individuals on sirolimus are allowed to be enrolled since the disease is so rare. A study approved by the CDMRP in 2010 (the TRAIL trial) failed to achieve adequate enrollment because of this issue. Importantly, individuals enrolled in this study are on unchanging doses of sirolimus.

Subjects will be instructed at the beginning of the study to report to the investigator any adverse physical or mental changes they experience and they will be asked about adverse events at each visit, including those experienced at the baseline visit prior to, during, or immediately following treatment. All such adverse events reported by the subjects or observed by the investigators will be captured in the study forms. If the event is deemed to be Serious, the serious adverse events procedures will be followed and the IRB, DSMB, HRPO and Novartis notified.

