## 6.1.3 Imatinib side effects

The most common side effects of imatinib include nausea, diarrhea, headaches, leg cramps, fluid retention, visual disturbances, rash, weight gain, and reduced number of blood cells (any cell line can be affected). Imatinib is an immune suppressant and increases risks of common and uncommon infections.

Severe systolic congestive heart failure is an uncommon but recognized side effect of imatinib and mice treated with large doses of imatinib show toxic damage to myocardiocytes. Hypoxemia has been noted in one individual with LAM.

Since imatinib is mainly metabolised via the liver enzyme CYP3A4, substances such as ketoconazole, itraconazole, clarithromycin, and grapefruit juice can increase the plasma concentration of the drug. Conversely, CYP3A4 inducers like rifampin and St. John's Wort reduce the drug's activity. These medications will be prohibited during the study. A known interaction between imatinib and sirolimus in which sirolimus levels rise will be monitored during the study.

Imatinib also acts as an inhibitor of CYP3A4, 2C9 and 2D6, increasing the plasma concentrations of simvastatin, cyclosporin, pimozide, warfarin, and metoprolol. Imatinib also reduces plasma levels of levothyroxin via an unknown mechanism. INR, Cholesterol, T4, and TSH will be measured during the study for all individuals.

An imatinib dose reduction to 200 mg daily will be permitted should a participant experience persistent side effects.

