## 7.3 Endpoints

**7.3.1 The primary efficacy analysis** will be the log transformed change in intrasubject plasma VEGF-D before and 1 month after initiation of monotherapy imatinib mesylate. Log transformation was needed in the MILES study because this serum concentration can often go quite high in some patients. VEGF-D will be obtained at baseline and at 28 and 56 days after initiation of imatinib. Note that this analysis will allow the use of sirolimus using and sirolimus naïve participants.

**7.3.2 Secondary endpoints** are obtained to test both efficacy and inform about quality of life. Quality of life questionnaire instruments are described in a later attachment as guided by the CDMRP program. Importantly, respiratory specific and general quality of life scores will be used in the study. Recently, the St Georges Respiratory Questionnaire (SGRQ) was retrospectively validated against four anchors in the MILES study and will be used as a secondary efficacy endpoint in the combined analysis of both stratified randomization populations. To minimize multiplicative analysis, 3 endpoints are chosen for combined population secondary endpoints: Intrasubject Change in FEV1 (ml), Intrasubject Change in FVC (ml), and Intrasubject Change in SGRQ (points) between the timepoints of Baseline and 1 month after initiation of monotherapy imatinib/placebo. The last secondary endpoint compares a 2 month treatment with imatinib/placebo in sirolimus naive participants on intrasubject change in log VEGF-D (pg/ml).

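### Section 5.6 makes a sirolimus-level rise an unblinding event, and imatinib is known to raise those levels, so unblinding is expected more often in the imatinib arm of a double-blind trial

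*Combined protocol and SAP*

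**What the plan says.** Sections 2.2 and 5.1 describe the trial as double blind. Section 5.6 sets up an unblinded team that "will be used to monitor sirolimus levels at 1 week and 1 month after baseline", and continues: "Levels that increase by > 50% will lead to sirolimus dose reductions that will unblind the study participants". These events go to the research monitor and the DSMB.

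Section 6.1.3 gives the reason for monitoring: "A known interaction between imatinib and sirolimus in which sirolimus levels rise will be monitored during the study". Section 5.4 applies the early check in both arms: "A 1 week trough sirolimus level and telephone call will be obtained on all subjects entering the study on sirolimus therapy". Of the 1-month visit, section 5.4 says: "Sirolimus will be discontinued if used at baseline".

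Section 7.3 defines the primary analysis as the "log transformed change in intrasubject plasma VEGF-D before and 1 month after initiation of monotherapy imatinib mesylate". It sets changes in FEV1, FVC and SGRQ over the same interval as secondary endpoints. For a baseline sirolimus user, monotherapy starts at the 1-month visit, so these outcomes are read at 2 months. Section 7 has no rule for analysing participants who have been unblinded.

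**The concern.** The trigger for unblinding is a quantity that the study drug itself moves. Loss of masking would therefore depend on treatment, and it would come before the main assessments.

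Spirometry and the walk test depend on effort, and SGRQ and mMRC are self-reported. Section 6.4.1 ends participation on symptom deterioration or a 10% fall in post-bronchodilator FEV1 or FVC, and it allows withdrawal for any reason. Section 2.1 reports that in the earlier placebo-controlled sirolimus trial most women did not reach the next visit after the drug was stopped. A participant who has just stopped sirolimus and knows whether she is taking imatinib or placebo may decide differently about staying, and staying determines whether she has a 2-month VEGF-D value.

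**Working it through.** **Stated figure.** The documents predict no number of unblindings, so there is nothing to reproduce. The calculation below is an illustration.

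**Inputs from the documents.** The threshold is a rise above 50%, checked at 1 week and 1 month (5.6). The direction of the interaction is upward on imatinib (6.1.3). Ten sets each of imatinib and placebo are prepared (6). On sirolimus use, section 6 says "it is estimated that 90% of individuals with LAM and low lung function are using this drug"; applied to 10 per arm this gives 0.9 × 10 = 9 users per arm. That is a population estimate, not an enrolment target. Section 7.1 expects only a majority.

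**Assumptions not in the documents.** Trough levels are lognormal with a within-person CV of 15% to 40%. The mean level ratio R is 1.0 on placebo and 1.25 to 2.0 on imatinib. There is no dose change after week 1.

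**Formula for one check.** With s² = ln(1 + CV²), P(rise > 50%) = 1 − Φ[(ln 1.5 − ln R) / (s√2)].

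Example at CV 20%: s = √ln(1.04) = 0.198 and s√2 = 0.280.
- Placebo, R = 1: 0.405 / 0.280 = 1.45, so P = 0.074.
- Imatinib, R = 1.25: (0.405 − 0.223) / 0.280 = 0.65, so P = 0.258.

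**Either check.** Both checks share one baseline level, so their joint probability was simulated (400,000 draws). Cells show week 1 / either check.

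| CV | Placebo, R = 1.0 | Imatinib, R = 1.25 | Imatinib, R = 1.5 | Imatinib, R = 2.0 |
|---|---|---|---|---|
| 15% | 0.027 / 0.049 | 0.194 / 0.305 | 0.500 / 0.667 | 0.914 / 0.974 |
| 20% | 0.074 / 0.126 | 0.258 / 0.390 | 0.500 / 0.667 | 0.848 / 0.942 |
| 30% | 0.164 / 0.264 | 0.330 / 0.480 | 0.500 / 0.667 | 0.756 / 0.884 |
| 40% | 0.228 / 0.352 | 0.369 / 0.526 | 0.500 / 0.666 | 0.701 / 0.844 |

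**Counts.** With 9 users per arm, crossings at either check number 9 × 0.305 = 2.7 to 9 × 0.974 = 8.8 on imatinib, against 9 × 0.049 = 0.4 to 9 × 0.352 = 3.2 on placebo. With a bare majority of users (11 of 20, about 5.5 per arm), they number 1.7 to 5.4 against 0.3 to 1.9. With 9 users, the chance of at least one imatinib crossing is never below 1 − (1 − 0.305)⁹ = 0.96.

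**Timing.** First crossings at 1 month make up only 0.060 to 0.167 on imatinib (0.5 to 1.5 of 9) and 0.022 to 0.123 on placebo (0.2 to 1.1 of 9). Week 1 supplies more than half of all crossings in every cell; the smallest share is 0.027 / 0.049 = 55%.

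**What a crossing reveals.** With equal arms, the chance that a participant who crosses is on imatinib runs from 0.526 / (0.526 + 0.352) = 60% to 0.974 / (0.974 + 0.049) = 95%. A dose change is informative about the arm but does not prove it.

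**The 1-month check.** In section 5.6 the level leads to a dose reduction, and the dose reduction unblinds. In section 5.4 sirolimus stops at that visit for every user, so there is no continuing dose to reduce. Section 5.6 neither exempts the 1-month level nor says what it triggers, so the two sections must be reconciled.

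**The case against.** A reader might infer that the 1-month check unblinds people for no purpose just before the monotherapy month. The documents do not show this. Under section 5.6 the dose reduction is what unblinds, and if none is possible at that visit the text can be read as causing no unblinding then. Nor is the 1-month level without use: section 5.5.1 uses visit levels to verify sirolimus status, and section 6.1.3 promises to monitor the interaction. What stands is an unresolved conflict between two sections.

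A reader might also infer that the primary VEGF-D result is biased directly. It is a laboratory assay, measured at the University of Cincinnati (4.2), and a participant's knowledge of her arm does not change the measurement. The route through exits is plausible, but its size is not known.

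Thirdly, it is tempting to say that the unblinding falls almost wholly on imatinib. At CV 40% and a 25% mean rise the split is only 53% against 35%. The direction holds in every scenario; a large imbalance does not.

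Other objections carry some weight. A participant has to be told to change her own sirolimus dose, so masking cannot be complete. Section 4.6 already regards group differences in lung function and quality of life as unlikely to be shown. Unblinding events are also reported to the monitor and the DSMB. That reporting, however, neither limits who learns the allocation nor says how these participants are analysed.

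**Conclusion.** The point holds for masking. By the plan's own account, unblinding is tied to a drug effect and should be more frequent on imatinib: about 31% to 97% of sirolimus users against 5% to 35% on placebo, mostly from the week-1 check. Those ranges rest on assumed variability and an assumed interaction size; only the direction comes from the documents. Participants not taking sirolimus at baseline are unaffected.

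The threat is to FEV1, FVC, SGRQ, walk distance and exit decisions, and through exits to the completeness of the 2-month VEGF-D data. An unblinded team already exists, so much of this risk can be avoided cheaply, and the change is worth making.

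**What to change.** 1. Reconcile sections 5.4 and 5.6 on what a 1-month level can trigger when sirolimus stops at that visit, and state that the level does not by itself lead to unblinding.
2. Replace the statement that a dose change unblinds with a masking rule. The unblinded team gives the participant any sirolimus instruction without disclosing the allocation. Levels, dose changes and allocation are withheld from the blinded assessors who carry out spirometry, walk tests and questionnaires or decide on exits. This covers the week-1 check, where most crossings arise.
3. Report sirolimus dose changes and true unblindings by arm, and keep all randomised participants in the main analyses. If a comparison without unblinded participants is shown, label it descriptive: it conditions on a treatment-related event after randomisation and would remove more imatinib than placebo participants.

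The cost is protocol wording and one table by arm. Some participants may still guess their arm from a dose change. No view is given on the sirolimus threshold or dose rule.

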## 6. ETHICAL CONSIDERATIONS

This study will be initiated only after a thorough review by the MUSC IRB, the Columbia University IRB, and the Human Research Protection Office (HRPO) of the US Army Military Department. A written informed consent will be obtained from every participant in which known side effects of imatinib are described. Participants may participate in this study and request that their biosamples be anonymized and/or not stored after the study analysis is complete.

An important consideration for this study is that sirolimus is not currently FDA approved for LAM. However, it is estimated that 90% of individuals with LAM and low lung function are using this drug and efforts are underway by [name], principal investigator of the MILES trial and medical director of the LAM Foundation to obtain FDA approval via his IND for sirolimus. This study is submitted because no study in LAM will advance in this rare disease population unless individuals on sirolimus are allowed to be enrolled since the disease is so rare. A study approved by the CDMRP in 2010 (the TRAIL trial) failed to achieve adequate enrollment because of this issue. Importantly, individuals enrolled in this study are on unchanging doses of sirolimus.

Subjects will be instructed at the beginning of the study to report to the investigator any adverse physical or mental changes they experience and they will be asked about adverse events at each visit, including those experienced at the baseline visit prior to, during, or immediately following treatment. All such adverse events reported by the subjects or observed by the investigators will be captured in the study forms. If the event is deemed to be Serious, the serious adverse events procedures will be followed and the IRB, DSMB, HRPO and Novartis notified.

An independent Data Safety Monitoring Board (DSMB) composed of 3 individuals (2 pulmonary specialists and one regulatory/statistical clinical trial specialist) will be established to provide independent benefit/risk oversight during the conduct of the study. The DSMB will: 1) Review the protocol and consent form prior to study initiation, 2) Evaluate Serious Adverse Events on an "as needed" basis and all adverse events on a quarterly basis, 3) Recommend discontinuation of the study in the event of the occurrence of Serious or Unexpected Adverse Events that are determined by the DSMB to pose a significant safety concern. The Chairperson of the DSMB will notify the HRPO and [name] who will in turn notify the FDA or other regulatory bodies of adverse safety outcome information sufficient to stop the study. This information will also be reported as part of required regulatory progress update reports [name], MS, will serve as independent research monitor in accordance with Department of Defense requirements. The research monitor will provide study oversight and will have the authority to take any action necessary, including stopping the research or

removing a subject, to protect the safety and well-being of human subjects until the IRB has a chance to assess the monitor's report.

[name] is a trained study coordinator who will be in charge of creating and maintaining the randomization list at MUSC. [name] is a trained study coordinator who will count and package study medication and placebo for both study sites, so that 10 sets of imatinib and 10 sets of placebo are prepared. [name] [name] will oversee the counting, packaging and sorting as a double check mechanism. [name] will ensure appropriate sorting of correct quantities of imatinb and placebo into two distinct groups. After this double check is complete, [name] will label the two distinct and counted groups (imatinib and placebo) as A and B and [name] will ensure that the labels have been accurately applied to the two distinct groups. Labels compliant with pharmaceutical standard of care will be applied. Five sets of A and 5 sets of B will be sent by FedEx to Columbia University for their 10 participants. At MUSC [name] will randomize the participant without knowledge of whether A and B are drug or placebo. According to the randomization assignment, the blinded assessors, PI [name] or [name] will dispense A or B to the participant. The label will contain space for the authorized blinded dispensing physician to write in the participant's name just prior to dispensing to the participant.

Columbia University will name a trained study team member to perform their randomization. Blinded assessor and co-investigator who will dispense medication at that site is [name]. The Columbia IRB will review and approve their plan and designation.

**Participation of children** is not allowed in this study because LAM does not cause clinical disease in this population.

**Participation of women and minorities** is encouraged, particularly since this disease only affects women. Sirolimus is pregnancy category C and imatinib is pregnancy category D. Pregnancy or intent to become pregnant or nurse during the 2 month study window and for 1 month afterwards is not allowed because of the safety risk of a category D medication. An adequate birth control method during these 3 months will be documented in all women of childbearing potential.

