## 6.3.1 Procedures for Adverse Events

Event, date of onset, severity, duration, and relationship to sirolimus or imatinb (if it can be determined) will be recorded on the study AE forms. All adverse events will be followed until they are adequately resolved or stabilized, or for 1 month following study completion, whichever comes first.

If an adverse event occurs during a study visit the study coordinator should first insure the participant receives any needed medical attention. If the study coordinator is notified by phone, the coordinator should confirm that the participant has received medical attention. The study coordinator should then notify the site Principal Investigator and complete the Adverse Event Form within seven days of learning of the event. Study coordinators will comply with local regulations and policies when notifying the institutional IRB.

The following general definitions for rating severity should be used for this study:

**Mild:** Awareness of signs or symptoms, but easily tolerated and transient; causing no loss of time from normal activities; symptoms would not require medication or a medical treatment; signs and symptoms are transient.

**Moderate:** Marked symptoms and discomfort severe enough to cause moderate interference with the subject's usual activities. Symptomatic treatment is possible.

**Severe:** Incapacitating with inability to do work or usual activities; signs and symptoms may be of systemic nature or require medical intervention and/or treatment. Hospitalization may be required or prolonged.

The relationship of an AE or SAE to the underlying disease or to the procedure will be attributed using the following definitions:

Not Related: There is no evidence that the event has a relationship to the drug(s).

**Possibly Related**: The event has a timely relationship to the drug(s) used. However, a potential alternative etiology may be responsible for the adverse event.

**Probably Related**: The event has a timely relationship to the drug(s) used and the causative relationship can clearly be established. No potential alternative etiology is apparent.

The number of subjects and observation time in this pilot study is insufficient to develop a composite index or statistical plan for the evaluation of safety endpoints for this study. Therefore, all adverse events, their timing, severity, and attribution will be reported in study reports.

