## 6.4 Measures to Protect the Participant

All participants will have laboratory monitoring of CBC, T4, TSH, Cholesterol, INR, Sirolimus level and complete metabolic panel (CMP) at baseline, 28 days, and 56 days. Side effects may receive imatinib dose reduction to 200 mg daily if persistent. Study withdrawal for side effects is permitted. All side effects will be graded and followed. Side effects suggestive of an infection will prompt cessation of subsequent doses of rapamycin and imatinib mesylate/placebo for 1 week until such symptoms are improved. Any worsening of symptoms would prompt evaluation. Decline in FEV1 or FVC of 10% would prompt end of study, study unblinding, and transition to usual clinical care. A study

coordinator will call each participant to check on how they are doing 1 week +/- 3 days and 2 weeks +/- 3 days after the baseline visit and 2 weeks +/- 3 days after the 1 month study visits.

Study related injuries are addressed in the MUSC Statements of the informed consent form. In the event of a study related injury, the participant should go immediately to the emergency room of the Medical University Hospital, or in case of an emergency go to the nearest hospital, and tell the physician on call that they are in a research study. The doctor should call the study doctor to make arrangements for treatment. If the study sponsor does not pay for treatment, the Medical University Hospital and the physicians who render treatment will bill the participant's insurance. If the insurance company denies coverage or insurance is not available, the participant will be responsible for payment of all services rendered.

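### All imatinib carries one letter and all placebo the other, and blinded assessors dispense by letter, so one assignment learned by a dispenser decodes every other participant whose letter that dispenser knows

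*Combined protocol and SAP*

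**What the plan says.** Section 5.1 describes the trial as double blind. Section 6 (Ethical Considerations) sets out packaging: 10 sets of imatinib and 10 of placebo are sorted into two groups, and a named staff member "will label the two distinct and counted groups (imatinib and placebo) as A and B". The letters are common to both sites: "Five sets of A and 5 sets of B will be sent by FedEx to Columbia University for their 10 participants". At MUSC the person who randomizes does not know what the letters mean, and one of two blinded assessors "will dispense A or B to the participant", writing the participant's name on the label. For Columbia the text reads "Blinded assessor and co-investigator who will dispense medication at that site is", followed by one name; that site's plan goes to its own IRB. No kit number or other participant-level code is described.

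Two places provide for unblinding during the study. Section 6.4 says: "Decline in FEV1 or FVC of 10% would prompt end of study, study unblinding, and transition to usual clinical care". Section 5.6 gives sirolimus levels to a separate unblinded team and says: "Levels that increase by > 50% will lead to sirolimus dose reductions that will unblind the study participants". It adds that these events go to the research monitor and into DSMB reporting. Section 6.1.3 supplies the link to treatment: "A known interaction between imatinib and sirolimus in which sirolimus levels rise will be monitored during the study".

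**The concern.** With only two codes, the blind is held in common rather than participant by participant. Once the meaning of one letter is known, so is the other, and the people holding the letters are the blinded assessors. An emergency or planned unblinding of one woman, which should cost the trial one blinded participant, can then cost it many.

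What is at stake is investigator judgement. Section 6.3.3 has the investigator assess how each SAE relates to each study treatment. Section 6.4.1 ends participation for worsening symptoms and lets the site PI remove a participant on safety grounds; at MUSC the PI is also one of the two dispensers. Departures before month 2 would cost final VEGF-D values in a trial of 20. Spirometry and walk-test effort could be affected only if the test operator knew the letter, and Section 5.5.2 names no operator.

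**Working it through.** **Inputs.** Sets per arm and per site, and who dispenses: Section 6. Planned enrolment by quarter: Section 5.2.1. Follow-up of 2 months: Section 5.1.

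**Counts in the plan.** Sets: 10 + 10 = 20; Columbia 5 + 5 = 10, leaving 5 + 5 = 10 for MUSC. Enrolment from Year 1 Q3 to Year 2 Q3 is 1, 2, 4, 2, 1 at MUSC and 0, 2, 5, 2, 1 at Columbia. Cumulatively this gives 1, 3 + 2 = 5, 7 + 7 = 14, 9 + 9 = 18 and 10 + 10 = 20, which reproduces the plan's cumulative row.

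**What one disclosure decodes.** Suppose an assessor knows the letters of k participants and learns the true treatment of one of them (the index participant). Both letters are then fixed, and the other k − 1 are decoded.
- Columbia, one planned dispenser: k is at most 10, so up to 9 others.
- MUSC, two possible dispensers: k = 5 on an even split (assumed) gives 4 others. If both dispense at all, k runs from 1 to 9, giving 0 to 8 others. If letters or the dispensing record are shared, k = 10 and 9 others are decoded. The documents do not say which applies.
- Unique kit numbers: no others are decoded. If a site uses its full 5 + 5, the best guess for each of the other nine is the opposite arm, right with probability 5/9 = 0.56 instead of 1.00.

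**Who can still be affected.** Only participants on study or yet to enrol matter. Take a disclosure at the end of a quarter. Still to enrol = 10 − cumulative enrolment at the site. Because follow-up (2 months) is shorter than a quarter, others on study number at most that quarter's enrolment less the index participant. MUSC figures assume shared letters.

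| End of | Columbia: to enrol | Columbia: others on study, at most | Columbia: sum | MUSC: to enrol | MUSC: others on study, at most | MUSC: sum |
|---|---|---|---|---|---|---|
| Year 1 Q4 | 10 − 2 = 8 | 2 − 1 = 1 | 9 | 10 − 3 = 7 | 2 − 1 = 1 | 8 |
| Year 2 Q1 | 10 − 7 = 3 | 5 − 1 = 4 | 7 | 10 − 7 = 3 | 4 − 1 = 3 | 6 |
| Year 2 Q2 | 10 − 9 = 1 | 2 − 1 = 1 | 2 | 10 − 9 = 1 | 2 − 1 = 1 | 2 |
| Year 2 Q3 | 10 − 10 = 0 | 1 − 1 = 0 | 0 | 10 − 10 = 0 | 1 − 1 = 0 | 0 |

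**The two routes compared.** Section 6.4 calls for unblinding and sets no limit on who receives the result, so a dispenser could be told an assignment directly. Section 5.6 keeps levels with a separate team; a dispenser would have to hear of a reduction and then reason from the interaction in Section 6.1.3. That makes imatinib probable, not certain.

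**The case against.** The case for leaving the plan alone has several sound parts.

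- *Safety output.* A reader might infer that attribution by an unblinded investigator is the trial's whole safety result, since no safety statistics are planned. Section 6.3.1 does not support that: it promises that "all adverse events, their timing, severity, and attribution will be reported in study reports". Laboratory monitoring (Section 6.4) and quarterly DSMB review of adverse events (Section 9.3) stand beside it. The investigator's duty to attribute is stated for SAEs, none of which is expected (Section 6.3.3); for other events the coordinator completes the form, and no one is named to judge the relationship. This objection stands and limits the harm.
- *Sirolimus reductions.* A reader might infer that any reduction reveals the assignment to the assessor. Section 5.6 speaks of participants being unblinded and puts a separate team in between. This also stands; the route is secondary.
- *Existing reporting.* Section 5.6 events are already reported, and SAE follow-up must say whether the blind was broken (Section 6.3.3). What is missing is any rule on whether the dispenser may be told.
- *Whole-trial decoding.* Because both sites share the letters, a reader might infer that all 19 other participants are exposed. Nothing says that assessors at one site know the letters dispensed at the other.
- *Columbia.* Its detailed plan is left to its IRB and is not in the documents, but its sets arrive already lettered.

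None of this supplies a participant-level code or stops the letters being decoded once a dispenser knows one assignment.

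**Conclusion.** The weakness is real and avoidable, and of minor to moderate severity. One true assignment learned by a dispensing assessor decodes up to 9 others at Columbia, and at MUSC between 0 and 9 depending on how dispensing and records are shared. The number who can still be influenced falls from at most 9 and 8 respectively at the end of Year 1 Q4 to none at the end of Year 2 Q3.

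This rests on enrolment following the planned table, on one dispenser at Columbia, and on the assessor knowing the index participant's letter. The documents give no rate for either unblinding route and do not say how often a dispenser would learn the result, so no probability is offered.

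A reader might go further and conclude that the primary endpoint is compromised. The documents do not support that: VEGF-D is measured at a University of Cincinnati laboratory (Section 4.2), so its values are largely protected. The exposure is SAE attribution and decisions on who stays to month 2.

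**What to change.** **Section 6.** Replace A and B with a unique kit number per participant, numbered in random order across treatments, so that the randomizer and dispensers see only a kit number. Existing staff who are already unblinded, and who neither dispense nor assess, should hold the kit-to-treatment key and apply the stratified assignment. At each enrolment they return the next unused kit of the assigned arm at that site, so kits need not be tied to a stratum in advance. The sponsor must confirm which role this is: Section 6 gives the MUSC randomization list to one coordinator and leaves Columbia's randomization to that site, and with names removed it cannot be verified that these roles are held by different people.

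**Sections 5.6 and 6.4.** State that dispensing assessors are not told an assignment unless that participant's care requires it. Extend the reporting in Section 5.6 to a log of every unblinding, including those under Section 6.4, recording who was told, when and why. A rule on disclosure alone would be cheaper, but it would leave the shared code in place if an assignment became known some other way.

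**Cost.** About 20 relabelled kits, one paragraph in Section 6, a short addition to each of Sections 5.6 and 6.4, and one contact per enrolment (about 20 in all) with an unblinded staff member, who must be reachable for both sites. Stock stays at 5 + 5 per site. No clinical rule, sample size or analysis changes. The index participant may still be unblinded; the change only stops the spread to others.
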